11.0 Statistical Analysis of the Study

Analysis

a. Sample Size Calculation – This is a pilot study to collect preliminary data using two interventions, i.e., trazodone or CBT, with unknown effects for chronic insomnia with objective short sleep duration. Based on our previous experience with interventional studies, we suggest that 10 subjects per group will be adequate to detect a difference of 20 minutes in objective sleep duration between the two treatment interventions. To allow for an anticipated 20% attrition rate, 24 subjects will be assigned to a study intervention to ensure complete data from 20 participants. The results of this study will allow the establishment of sample size for any future studies. Our statistical consultant in this study is [name].

b. Analytic Plan

Specific Aim 1: Examine the Effect of Trazodone vs. CBT for the Primary Outcome Variables (objective and subjective sleep duration) in Patients with Chronic Insomnia with Objective Short sleep Duration

Throughout the analysis, we will compare the differences (end of the interventional study baseline) between the two groups of the outcome of interest (e.g., total sleep time).

Total Sleep Time, Polysomnography: Both at baseline and the end of the intervention, polysomnography will be measured for 2 consecutive nights. We will calculate the time-specific difference from the baseline to the end of intervention. Then, we will compare the two treatment conditions with respect to the overall mean change across all time points (“difference of difference”) using the two-sample t-test. Alternatively, repeated measures analysis of variance (ANOVA) will be used to compare treatment conditions with respect to polysomnographic total sleep time changes from baseline. The time and treatment condition main effects as well as interaction between time and treatment condition will be tested. Adjustments for multiple comparisons across different time points and between intervention groups will be performed. Potential confounders and interaction between treatment condition and confounder will also be examined. In the event that the distribution of polysomnographic total sleep time are not consistent with the assumptions of normality required for ANOVA, attempts will be made to find suitable transformation.

Total Sleep Time, Actigraphy: Both at baseline and the end of the intervention, actigraphy will be measured for 2 weeks. We will calculate the time-specific difference from the baseline to the end of intervention. Then, we will compare the two treatment conditions with respect to the overall mean change across all time points (“difference of difference”) using the two-sample t-test. Alternatively, repeated measures analysis of variance (ANOVA) will be used to compare treatment conditions with respect to actigraphic total sleep time changes from baseline. The time and treatment condition main effects as well as interaction between time and treatment condition will be tested. Adjustments for multiple comparisons across different time points and between intervention groups will be performed. Potential confounders and interaction between treatment condition and confounder will also be examined. In the event that the distribution of actigraphic total sleep time are not consistent with the assumptions of normality required for ANOVA, attempts will be made to find suitable transformation.

Total Sleep Time, sleep diary: Both at baseline and the end of the intervention, subjective sleep duration will be measured with a 2-week sleep log. We will calculate the time-specific difference from the baseline to the end of intervention. Then, we will compare the two treatment conditions with respect to the overall mean change across all time points (“difference of difference”) using the two-sample t-test. Alternatively, repeated measures analysis of variance (ANOVA) will be used to compare treatment conditions with respect to subjective total sleep time changes from baseline. The time and treatment condition main effects as well as interaction between time and treatment

condition will be tested. Adjustments for multiple comparisons across different time points and between intervention groups will be performed. Potential confounders and interaction between treatment condition and confounder will also be examined. In the event that the distribution of subjective total sleep time are not consistent with the assumptions of normality required for ANOVA, attempts will be made to find suitable transformation.

Specific Aim 2: Examine the Effect of Trazodone vs. CBT on the Secondary Outcome Variables (insomnia severity, daytime functioning, stress, inflammation and insulin sensitivity) in Patients with Chronic Insomnia with Objective Short sleep Duration

Subjective sleep quality and insomnia severity: Both at baseline and the end of the intervention, self-reported sleep quality (PSQI) and insomnia severity (ISI) will be measured. We will calculate the time-specific difference from the baseline to the end of intervention. Then, we will compare the two treatment conditions with respect to the overall mean change across all time points (“difference of difference”) using multivariate repeated measures analysis of variance (MANOVA) to compare treatment conditions with respect to all measures of subjective sleep quality and insomnia severity changes from baseline. The time and treatment condition main effects as well as interaction between time and treatment condition will be tested. Adjustments for multiple comparisons across different time points and between intervention groups will be performed. Potential confounders and interaction between treatment condition and confounder will also be examined. In the event that the distribution of subjective sleep quality and insomnia severity measures are not consistent with the assumptions of normality required for MANOVA, attempts will be made to find suitable transformation.

Sleepiness, fatigue, and mood: Both at baseline and the end of the intervention, self-reported sleepiness (ESS), fatigue (POMS-F and MFI) and mood (BDI-II, BAI, and HAD-S) will be measured. We will calculate the time-specific difference from the baseline to the end of intervention. Then, we will compare the two treatment conditions with respect to the overall mean change across all time points (“difference of difference”) using multivariate repeated measures analysis of variance (MANOVA) to compare treatment conditions with respect to all measures of sleepiness, fatigue, and mood changes from baseline. The time and treatment condition main effects as well as interaction between time and treatment condition will be tested. Adjustments for multiple comparisons across different time points and between intervention groups will be performed. Potential confounders and interaction between treatment condition and confounder will also be examined. In the event that the distribution of sleepiness, fatigue, and mood measures are not consistent with the assumptions of normality required for MANOVA, attempts will be made to find suitable transformation.

Stress, inflammation, and insulin sensitivity: Both at baseline and the end of the intervention, saliva cortisol, TNF α , TNFr1, IL-6, and the fasting glucose to insulin ratio (G/I) will be measured. We will calculate the time-specific difference from the baseline to the end of intervention. Then, we will compare the two treatment conditions with respect to the overall mean change across all time points (“difference of difference”)

using multivariate repeated measures analysis of variance (MANOVA) to compare treatment conditions with respect to all measures of stress, inflammation and insulin sensitivity changes from baseline. The time and treatment condition main effects as well as interaction between time and treatment condition will be tested. Adjustments for multiple comparisons across different time points and between intervention groups will be performed. Potential confounders and interaction between treatment condition and confounder will also be examined. In the event that the distribution of stress, inflammation and insulin sensitivity measures are not consistent with the assumptions of normality required for MANOVA, attempts will be made to find suitable transformation.

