A. Primary outcomes: we hypothesize that **trazodone** will result in a greater improvement of objective sleep duration (assessed by PSG and actigraphy) and subjective nighttime sleep than CBT in insomniacs with objective short sleep duration.

B. Secondary outcomes: we hypothesize that **trazodone** compared to CBT will result in a greater improvement of daytime fatigue, cortisol, inflammatory markers, and insulin sensitivity in insomniacs with objective short sleep duration.

The accomplishment of the above-described objectives will create the basis for the development of novel and specific treatments for chronic insomnia, and improve our understanding of the pathophysiology of this heterogeneous disorder.

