4.0 Inclusion and Exclusion Criteria

Study Population – A total of 70 men and women will be screened for inclusion in this study. 24 men and women with chronic insomnia will be enrolled to receive study therapy over a 3-month period. This study will focus on adult men and women (30- 60 years old) with a chronic complaint of insomnia and concomitant objective short sleep duration, based on both clinical and polysomnographic criteria. All subjects will meet the Research Diagnostic Criteria (RDC) for insomnia (Edinger et al, 2004) and will demonstrate < 6 hours of sleep, as assessed by polysomnography (Table 1). In addition, they should meet the criteria for duration for more than one year because this is the population that is associated with hypercortisolemia and medical morbidity as shown in our previous experimental and epidemiological studies.

Table 1. Research diagnostic criteria (RDC) for insomnia.

Insomnia disorder
A. The individual reports one or more of the following sleep related complaints: 
 1. difficulty initiating sleep, 2. difficulty maintaining sleep, 3. waking up too early, or 4. sleep that is chronically non-restorative or poor in quality.
B. The above sleep difficulty occurs despite adequate opportunity and circumstances for sleep.
C. At least one of the following forms of daytime impairment related to the nighttime sleep difficulty is reported by the individual: 
 1. fatigue/malaise; 2. attention, concentration, or memory impairment; 3. social/vocational dysfunction or poor school performance; 4. mood disturbance/irritability; 5. daytime sleepiness; 6. motivation/energy/initiative reduction; 7. proneness for errors/accidents at work or while driving; 8. tension headaches, and/or GI symptoms in response to sleep loss; and 9. concerns or worries about sleep.

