6.0 Study Procedures

Screening phase

The subjects' diagnoses of insomnia and other sleep disorders will be established by a clinical sleep history conducted by a clinical psychiatrist or psychologist who practices sleep medicine. The subjects that meet the research diagnostic criteria (RDC) for insomnia will be included in the study (see Table 1). The subjects' sleep patterns will be assessed via a sleep diary and actigraphy (for two weeks) prior to their visit to the sleep lab. Each subject will be monitored continuously for eight hours for one night in the sleep unit of the GCRC according to standard techniques (Rechtschaffen and Kales, 1986; Iber et al, 2007.). The first night will serve as a screening night for the presence of sleep apnea or periodic limb movements, and an adaptation night to control for "first night" effects. Prior to or during their visit to the sleep unit, the participants will be assessed for psychiatric disorders using a Structured Clinical Interview for DSM-IV, the Mini International Neuropsychiatric Interview (MINI ; Sheehan et al, 2006).

Figure 1. Screening phase, randomization of patients with insomnia.

Randomized Clinical Trial of Trazodone vs. CBT

a. Baseline measures – Following the screening night, the subjects that will enter the randomized trial will be monitored in the sleep laboratory continuously for 8 hours for 2 consecutive nights according to standard techniques (Rechtschaffen A, Kales A, 1968) (Table 3). Following the first night in the sleep laboratory, the participants will be admitted to GCRC for a complete semi-structured medical history and physical examination. Blood, urine and saliva will be collected and an electrocardiogram (EKG) will be performed. A pregnancy test will be performed on females of child bearing age. Following the second night in the sleep laboratory, daytime sleepiness and fatigue, nighttime sleep quality and quantity, and mood will be assessed subjectively with standardized self-reported questionnaires.

b. Randomization Scheme for Intervention – Subjects will be randomly assigned by our statistician into either a trazodone or a CBT program. Between the two intervention groups, we will attempt to have similar BMI, gender, and age distributions. If a patient is randomized and enters the randomization trial, then the patient will be considered enrolled in the study.

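### Minor: assigning 24 patients at the stated 20% attrition gives 19.2 expected completers, not the 20 that the sample-size paragraph promises

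*Combined protocol and SAP*

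**What the plan says.** Section 11.0 (a. Sample Size Calculation) sets the size of the trial in one paragraph. It opens with "This is a pilot study to collect preliminary data using two interventions". It then says, citing the team's previous experience, that "10 subjects per group will be adequate to detect a difference of 20 minutes in objective sleep duration" between the interventions. The number to recruit follows: "To allow for an anticipated 20% attrition rate, 24 subjects will be assigned to a study intervention to ensure complete data from 20 participants".

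Other sections make clear what the 24 counts. Section 4.0 (Study Population) says that "24 men and women with chronic insomnia will be enrolled to receive study therapy over a 3-month period", and gives a separate figure of 70 to be screened. Section 6.0 (b. Randomization Scheme for Intervention) defines enrolment by randomisation: "If a patient is randomized and enters the randomization trial, then the patient will be considered enrolled in the study". Section 2.0 also gives 24 as the size of the randomised trial.

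**The concern.** An attrition rate is ordinarily the share of those who start that is later lost. Here those who start are the 24 randomised patients. Screening failures are counted separately, so they cannot be what the 20% refers to. On that base, the stated rate and the stated 24 do not produce the stated 20.

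The target matters because 20 completers is the 10 per group on which the paragraph rests its claim about detecting 20 minutes. If the inflation is wrong, the plan expects to finish below its own target. The question is by how much, and whether that has any practical effect.

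**Working it through.** **Inputs from the documents**
- Assigned: 24 (sections 2.0, 4.0 and 11.0)
- Anticipated attrition: 20% (section 11.0)
- Completers wanted: 20, as 10 per group (section 11.0)
- Difference of interest: 20 minutes (section 11.0)
- Planned comparison of change: two-sample t-test, with repeated measures ANOVA as the alternative (section 11.0, Analytic Plan)

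**Step 1. Reproduce the plan's figure.** Multiplying the completers by one plus the rate gives 20 x (1 + 0.20) = 24. This matches exactly.

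**Step 2. Apply the rate to those assigned.** The number needed is completers / (1 - rate) = 20 / 0.80 = 25. The difference from the plan is 25 - 24 = 1 patient.

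**Step 3. Expected completers from 24.** 24 x 0.80 = 19.2. The expected loss is 24 x 0.20 = 4.8, against the 24 - 20 = 4 that the plan has room for. The shortfall is 20 - 19.2 = 0.8 of a completer.

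**Step 4. Attrition that 24 can absorb.** 4 / 24 = 16.7%.

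**Step 5. Cost in power.** The documents give no standard deviation (SD) of change, alpha or sidedness. I assume a two-sided 5% two-sample t-test with no multiplicity adjustment, and I vary the SD. Power comes from the noncentral t distribution with noncentrality 20 / (SD x sqrt(1/n1 + 1/n2)) and n1 + n2 - 2 degrees of freedom.

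| Assumed SD of change (min) | 10 and 10 completers | 9 and 10 completers | Loss (points) |
|---|---|---|---|
| 10 | 98.8% | 98.4% | 0.4 |
| 12 | 94.1% | 92.7% | 1.4 |
| 15 | 80.5% | 78.1% | 2.4 |
| 17.5 | 67.6% | 65.0% | 2.6 |
| 20 | 56.2% | 53.7% | 2.5 |
| 30 | 29.2% | 27.8% | 1.4 |
| 40 | 18.5% | 17.7% | 0.8 |

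The loss peaks at about 2.6 points, near an SD of 17 to 18 minutes. The table measures the cost of one missing completer. The SDs are assumptions, so it does not show the power that the trial will have.

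**The case against.** The strongest reply is that this is a slip of one patient in a pilot. The 24 is reproduced exactly by a common shortcut, no confirmatory decision hangs on it, and a sentence about anticipated attrition is a planning statement and not a guarantee. Nearly all of this stands. It fixes the grade at minor and is the reason to leave 24 alone. It does not make the sentence right: the rate, the number assigned and the number completing still disagree, and rounding does not help, because 4.8 expected losses exceed 4.

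Three stronger readings are tempting.

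- **A reader might infer that the slip leaves the trial unlikely to reach its target.** If patients drop out independently at 20%, the chance that at least 20 of 24 complete is 46%, and the chance of at least 10 in both arms is 31% with 12 per arm assumed. Correct inflation gives only 62% with 25 assigned, and 56% for both arms with 13 per arm. Much of the shortfall from certainty therefore belongs to the verb *ensure*, which would overstate the case at 25 or 26 as well.
- **A reader might infer that 10 per group has been shown too small for 20 minutes.** It has not. No SD of change appears in the documents, so the claim can be neither confirmed nor refuted from them. The paragraph also omits alpha, sidedness and power. It does not say which measure the 20 minutes concerns, although section 2.0 describes "objective sleep duration (assessed by PSG and actigraphy"). These are gaps in reporting, not errors.
- **A reader might infer that the slip will carry into later trials.** Sections 8.0 and 11.0 say that the results and data of this study will inform future designs. They do not say that this paragraph's attrition allowance will.

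**Conclusion.** Wrong as written, and minor. At the stated 20% attrition, 24 assigned patients give 19.2 expected completers and not 20. The 24 fits a loss of 16.7%, and a 20% loss calls for 25. That conclusion needs only the plan's own figures and the reading, supported by sections 4.0 and 6.0, that the 24 are the randomised patients.

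The effect is 0.8 of an expected completer and about 2.6 points of power or less. The power figure rests on the assumed two-sided 5% t-test and on comparing 10 and 10 completers with 9 and 10. The documents do not support calling 24 inadequate, the trial underpowered, or the 20-minute statement false.

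**What to change.** Keep 24 and reword the attrition sentence in section 11.0 a. For example: *Twenty-four patients will be randomised. This leaves room for 4 losses (16.7%) with 20 completing; at the anticipated attrition of 20%, about 19 are expected to complete.* The verb *ensure* goes.

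The cost is one sentence. The number randomised, the procedures, the analyses and the reporting commitments do not change. What is lost is the assurance of 20 completers, which the figures never gave.

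As an optional reporting note, the sponsor could add the SD of change, measure, alpha, sidedness and power behind the 20-minute statement, if the previous experience it cites supplies them. I would not write a conditional SD threshold into the plan in their place. That would bring in an alpha that the documents never state, and it would ignore the multiplicity adjustments that the Analytic Plan promises.

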Our participants will be middle-aged adults since objective sleep duration significantly correlates with age in an inverse manner. We will not exclude insomniacs with minor forms of anxiety or depression, i.e., dysthymic disorder, since these conditions are highly comorbid in chronic insomniacs (Buysse et al, 1993; Kales and Kales, 1984; Buysse et al, 1994a; Buysse et al 1994b). However, insomniacs with a current diagnosis of a major mental disorder, i.e., schizophrenia, major depression, will be excluded from the study because these conditions are associated with the primary outcome variables of this study. In addition, we will exclude subjects with morbid obesity (BMI > 39) because, at this level, obesity is frequently associated with frequent sleep pathology, i.e., apnea, EDS, and significant medical morbidity (Vgontzas et al, 1994; Vgontzas et al, 1998).

Participants with an apnea/hypopnea index (A/HI) > 5 or periodic limb movements > 5 per hour of sleep will be excluded from the study. Also, subjects with a primary disorder of EDS, e.g., narcolepsy, or subjects with a history of shift work or circadian disorder will be excluded from the study (Vgontzas and Kales, 1999; Roehrs et al, 2005; Boggild and Knutsson, 1999) (Table 2).

Table 2. Inclusion/exclusion criteria.

Inclusion	Exclusion
Chronic insomnia (RDC) with a duration \geq 1 year Objective short sleep duration (< 6h) BMI < 39 Age range: 30-60 Equal number of men and women	Major mental illness Substance abuse/dependence Sleep apnea (apnea/hypopnea index \geq 5) PLMD (periodic limb movements \geq 5) Objective normal sleep duration (\geq 6h) Primary disorders of EDS, i.e., narcolepsy Shift work or circadian disorders Diabetes, chronic renal failure, hepatic insufficiency, chronic heart failure Current use of hypnotics or sleep inducing sedative antidepressants

RDC = research diagnostic criteria; PLMD = periodic limb movements disorder

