Subjects treated for diabetes or suffering from chronic renal failure or hepatic insufficiency or chronic heart failure will be excluded from the study. Also, because of the known effects of steroids on sleep, subjects on those medications will be excluded from the study. A family history of diabetes will be recorded during the medical history and physical examination and controlled within our analyses. Also, the potential effects of other medications or substances, such as alcohol or smoking, will be controlled within our analyses. Subjects with a diagnosis of substance abuse or dependence will be excluded from the study due to the potential effects of these substances on sleep and metabolism. Patients should be free of hypnotic use or sedative antidepressants administered at bedtime to improve sleep for one month before entering the study. Finally, patients using psychotropic medications, i.e., SSRI, who do not meet the criteria for a current major psychiatric disorder, and have continuous complaints of insomnia, will be included in the study. This is because a large portion of insomniacs consist of depressed individuals whose depression improved but still they have complaints of chronic insomnia. Potential confounding effects of medication on some of the outcome measures, i.e., objective sleep duration, will be dealt with in the analysis

Women and Minority Inclusion – In this project, we will include middle-aged men and women 30- 60 because they represent the majority of patients with insomnia in the general and clinic population. Women who are pregnant or breastfeeding will not be enrolled in the study. We plan to recruit about 21% of subjects belonging in minority groups. The racial and ethnic distribution shown in the Targeted/Planned Enrollment Table reflects the general demographics of our region. Minorities will be recruited from our clinics as well as through advertisements in papers with large groups of minority readers, such as Harrisburg, PA and Lebanon, PA.

IRB Protocol No. 35933
Version Date: 11/10/2015

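### Cheap improvement: name baseline total sleep time as a covariate in the primary comparisons. At 10 per arm this is often, not always, more precise than the planned change-score t-test.

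*Combined protocol and SAP*

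**What the plan says.** Section 11.0 b (Analytic Plan) gives near-identical text for polysomnographic (PSG), actigraphic and diary TST. A change from baseline to the end of intervention is formed, and then "we will compare the two treatment conditions with respect to the overall mean change across all time points" by a two-sample t-test. A second route follows for each outcome; for PSG it reads "Alternatively, repeated measures analysis of variance (ANOVA) will be used to compare treatment conditions with respect to polysomnographic total sleep time changes from baseline". In both routes baseline enters only by subtraction.

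Baseline TST is scheduled for all three measures (section 6.0, Table 3; section 11.0 b). It is not listed as a covariate. Section 4.0 says that family history of diabetes, other medications, alcohol and smoking will be controlled for, and of medication it says "Potential confounding effects of medication on some of the outcome measures, i.e., objective sleep duration, will be dealt with in the analysis". Section 11.0 b adds only that unspecified potential confounders will be examined.

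Section 11.0 a plans for 10 completers per group, 24 assigned, and a difference of 20 minutes in objective sleep duration. It calls the study a pilot.

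**The concern.** Subtracting baseline fixes the slope of follow-up on baseline at 1. ANCOVA estimates that slope from the data. When the true slope is well below 1, which is what regression to the mean produces, subtraction over-corrects and adds noise from the baseline measurement to the treatment comparison. With about 20 completers, precision is scarce, and a covariate that is already measured could narrow the interval for almost nothing. What is at stake is the width of the confidence interval for the TST difference, not the validity of the test.

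**Working it through.** **The plan's own figure.** Section 11.0 a gives 10 per group for 20 minutes without an SD, alpha, sidedness or power, so it cannot be reproduced. Assuming two-sided 0.05 and 80% power, the t distribution with 18 df implies an SD of change of about 15.1 min. The 24 assigned equals 20 × 1.2 (20/0.8 would be 25).

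**Inputs.** From the documents: n = 10 completers per arm, so N = 20. Assumed, because the documents are silent: rho, the baseline-to-month-3 correlation, 0.3 to 0.9; and k, follow-up SD divided by baseline SD, 1 to 1.5.

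**Formulas.** With baseline SD s and a randomised comparison:
- Change score: variance = (2/n) s² (1 + k² − 2·rho·k).
- ANCOVA: expected variance = (2/n) s² k² (1 − rho²) × (N − 3)/(N − 4). The last factor is the price of estimating the slope, 17/16 = 1.0625 at N = 20.
- Ratio, ANCOVA to change score = [k²(1 − rho²)] / [1 + k² − 2·rho·k] × 17/16.

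Denominator minus numerator of the bracketed fraction is (1 − rho·k)², which is never negative. The fraction is therefore at most 1, and the ratio of expected variances is at most 1.0625. That worst case occurs when the slope rho·k equals 1.

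**Results at 10 per arm.**

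| k | rho 0.3 | rho 0.5 | rho 0.7 | rho 0.9 |
|---|---|---|---|---|
| 1 | 0.69 | 0.80 | 0.90 | 1.01 |
| 1.25 | 0.83 | 0.95 | 1.04 | 1.01 |
| 1.5 | 0.93 | 1.02 | 1.06 | 0.83 |

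Example: k = 1.5, rho = 0.5 gives 1.6875/1.75 × 1.0625 = 1.02. At k = 1 the ratio is (1 + rho)/2 × 17/16, so break-even is rho = 32/17 − 1 = 0.88. Simulation with 40,000 trials per setting agrees with these values.

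**Single trials.** At k = 1 the mean width of the ANCOVA 95% interval, relative to that of the t-test, is 0.83, 0.90, 0.95 and 1.01 across the four rho values. The ANCOVA interval is nevertheless the wider one in about 10%, 20%, 38% and 63% of simulated trials. Over k from 1 to 1.5, its estimated variance exceeds 1.0625 times that of the change score in about 5% to 44% of trials.

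**Power, for scale** (noncentral t, 17 df for ANCOVA, k = 1, rho 0.3, 0.5, 0.7, 0.9). At SD of change 15.1 min, power goes from 80% to about 92%, 88%, 84% or 79%. At 30 min it goes from 29% to about 40%, 35%, 32% or 29%.

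**The PSG entry rule.** Section 4.0 requires that patients "will demonstrate < 6 hours of sleep, as assessed by polysomnography", without saying which night decides. Selecting on PSG sleep can reduce baseline spread and so raise k. I assumed a pre-selection mean of 330 to 390 min, SD 60, and rho 0.5 between baseline and month 3, kept values under 360 min, and applied the formula to the selected k and rho:
- A separate screening night qualifies the patient, with equal correlations between all visits: k about 1.00, ratio 0.74 to 0.76.
- A separate screening night, with screening-to-baseline correlation 0.8 to 0.9: k 1.14 to 1.42, ratio 0.83 to 0.90.
- The same value is both entry value and baseline: ratio about 0.91 to 0.98 (at mean 360: k = 1.52, rho = 0.33, ratio 0.95).

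The rule acts on PSG, so it does not directly truncate the actigraphy and diary baselines.

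**The case against.** The strongest reply is that this is a preference between two valid analyses in a labelled pilot. That stands. A reader might infer that the change-score t-test is biased or wrong; the documents do not support this. Under randomisation it is unbiased, and with complete data it matches the treatment main effect of the ANOVA on changes.

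Second, the sign of the gain cannot be fixed from the documents, because neither rho nor the SDs are given. This also stands. The ratios above run from 0.69 to 1.06 before the entry rule is considered, so a claim that ANCOVA is always more precise would go too far. The 17/16 bound is likewise a statement about expected variance and does not cap the loss in any one trial.

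Third, the sentence on potential confounders does not rule out baseline TST. True, but it does not specify it either, and it leaves the choice open until the data are in hand.

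A further tempting reading starts from "The results of this study will allow the establishment of sample size for any future studies" and infers that ANCOVA is needed to size a later trial. It is not. The SDs and the baseline correlation can be computed from the same data whichever primary model is named.

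**Conclusion.** The point holds as an optional, low-cost improvement. Baseline TST is collected and is not a named covariate in any of the three primary TST comparisons. With equal spread at both visits, ANCOVA has the smaller expected variance for any rho below about 0.88, by about 31% at 0.3, 20% at 0.5 and 10% at 0.7. The advantage shrinks or turns into a small loss if follow-up spread is clearly larger than baseline spread and the slope is near 1. For PSG at rho 0.5 the expected gain is roughly 10% to 26% if a separate screening night decides entry, and 2% to 9% if the entry value is also the baseline. All of this rests on assumed rho, SDs and pre-selection mean, and on 10 completers per arm. The low power remains either way.

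**What to change.** In section 11.0 b, name one primary model for each TST outcome: an ANCOVA of the month-3 value on arm and baseline TST, with one mean value per person per visit. For actigraphy, where the text now reads "actigraphy will be measured for 2 weeks. We will calculate the time-specific difference from the baseline to the end of intervention", and for the diary, that is the mean over all valid days; with complete data it gives the same mean change as day-by-day pairing. Report the adjusted difference with its 95% confidence interval. Keep the change-score t-test as a sensitivity analysis.

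The cost is SAP wording with no new data: one residual df (17 against 18), and an expected-variance loss of at most 6.25% at 10 per arm.

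Two neighbouring matters should be raised separately: whether BMI, gender and age (section 6.0 b) are used in the allocation and should be adjusted for, and which laboratory nights count as screening, adaptation and baseline, where the screening text and the polysomnography text of section 6.0 differ.
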